Fig. 3: Timeline of TIMCI research in Kenya and Senegal. **Pre-post study:** comparing clinical care of children in a pre-intervention period ('baseline') with a post-intervention period ('implementation'). **Pilot** – 2 to 4 facilities in parallel to baseline, to refine the intervention. The pre-post study dataset will be collected in these facilities, along with SPA and process mapping, caregiver IDIs and HCP IDIs. **SPAs** – cross-sectional assessments in 8-10 facilities comprising of observations of consultations of sick children, exit interviews with caregivers, interviews with HCPs and facility assessments. **Process-mapping and time-flow** – during baseline, early and late implementation. **Qualitative studies with caregivers and with HCPs** – at pilot facilities (IDIs only) and across the implementation period to understand change over time. IDIs will also take place in the baseline/pre-intervention period. **Key stakeholders** – KIs during baseline / pilot, early and late implementation. **All intervention facilities** – PATH M&E data, ePoct+ clinical consultation data, Health Management Information System data. **Cost and modelled cost-effectiveness:** cost data will be collected prior to intervention and on start-up costs, and again during implementation with final data collection to capture any missing information. **Abbreviations:** SPA – service provision assessments; IDIs – in-depth interviews; FGDs – focus group discussions; KIs – key informant interviews; HCPs – healthcare providers

The intervention will be implemented in approximately 60 health facilities providing primary care services. Pre-post, mixed-method and costing studies will be conducted in only a sub-sample of these facilities, with triangulation across studies to generate in-depth insights into

implementation. Routine data from non-study facilities will be extracted for analysis of the wider programme, including from the health management information system (HMIS), anonymised routine clinical data from the CDSA, and PATH project data.

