In addition to pulse oximetry, healthcare providers in the pulse oximeter plus Clinical Decision Support Algorithm (CDSA) will be guided throughout their medical consultations by an algorithm called ePoct+ and developed by Swiss TPH in collaboration with Unisanté/Wavemind (Lausanne, Switzerland).

Healthcare providers will use ePoct+ for the assessment, diagnosis and management of all sick children 0 – 59 months of age (i.e. only excluding those coming for routine immunisation /

growth check visits who are not reported to be unwell). In case a child comes back to the facility during the same disease episode, ePoct+ can be used to manage the child in the same way as during the baseline visit, as the algorithm takes into account duration of symptoms and previous treatments provided.

MedAL-R, the front-end application developed by Unisanté/Wavemind to implement ePoct+ is available for Android tablet or PC. The application can be deployed in health facilities in a standalone mode or a multi-device mode to facilitate the collaboration of several healthcare providers and storage of information in the patient's medical records. In the context of this study, MedAL-R will be deployed on tablets. The choice of a standalone / multi-device setting depends on discussions with the country MoHs.

The clinical algorithm will be adapted to reflect national guidelines for the management of children 0-59 months of age in primary care (based on IMCI and additional relevant case management guidelines for children 0 – 59 months). An expert group will be established and consulted in each country using a Delphi method approach and / or nominal group technique to validate the clinical algorithm.

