6.7 Recruitment

To reach the required sample size, and to ensure data collection across different seasons, it is estimated that recruitment will take place over 15 months. As we intend to validate eligibility and recruitment rate estimates in the pre-intervention phase, we may either recruit additional facilities or slightly increase the study duration if necessary. Participants will be recruited during working hours, Monday to Friday, though evenings and weekends may be included if high volumes of patients attend at those times (depending on country and facility type).

Child and caregiver participants will be recruited for the SPA and time-flow observations on the relevant study assessment days consecutively until the sample size requirements detailed above have been met. Children and their caregivers will be enrolled to these studies at the same time as they are enrolled to the pre-post study. Longer assessment periods will be required for low-volume facilities. All healthcare providers providing care for children under 5 years of age and present at facilities during SPA assessments will be invited to participated in the SPA interview.

Participants in the qualitative studies will be recruited as follows:

Caregivers for IDIs and FGDs will be selected based on pre-defined queries (e.g. based on information from the database) after Day 7 follow-up has occurred in order to identify potential participants within a selected geographical area. During the call, caregivers will be asked for their verbal assent to be contacted by a person responsible for the recruitment of participants for qualitative studies. Of those caregivers, who agreed to be contacted, a list will be generated for the recruiter with basic socio-demographic details (divided into referred and

not referred for IDIs) of double the number of participants required (to allow for unreachable participants or refusals to participate) for the time point in question. The qualitative researcher will then contact participants by phone to arrange IDIs or FGDs. If recruitment with this strategy proves challenging, individuals may be approached directly at facilities to arrange a follow-up in the community after 7 days or at the community level (i.e. by a community health worker).

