7.1.1 Quasi-experimental pre-post study

For each participant enrolled in the quasi-experimental pre-post study, data will be captured during the pre- and post-intervention periods according to the different assessments and Case Report Forms (CRFs) described in the visit schedule displayed in **Tab. 4**. A description of the variables collected in each CRF is available in the appendix.

Health facility visits

Quantitative research assistants will use an EDC mobile application to enter the research data of enrolled participants. The quantitative research assistant will collect from the caregiver screening information, information on care seeking behaviour, transport and costs, and clinical presentation and medical history. A number of in-depth sociodemographic and household variables will also be collected either as surrogate measures of household wealth, or known to be associated with health-seeking behaviour and / or child mortality (including maternal

education). Household wealth indicators were selected from DHS and other surveys in the study countries as those which best estimate wealth index that can be directly collected from the mother / caregiver and with a reasonable time vs. reliability trade-off. Data on laboratory investigations (if performed), final diagnosis, prescribed medication, referral or follow-up advice will be extracted from clinical notes and / or facility registers. Quantitative research assistants will seek clarification from healthcare providers only in cases where these variables are not clear from the records. Personally identifiable information (PII), including participant's name and date of birth, as well as caregiver's phone number and physical address, will be collected for linking data and detecting possible duplicates and carrying out the study follow-up.

During the post-intervention period, the research data of participants enrolled in the study will be linked with their CDSA consultation data. Additional information on oxygen saturation will be collected as recorded in clinical notes and / or facility registers. Pulse oximeter device savings will be cross-checked by quantitative research assistants at the end of the consultation where possible.

Follow-up

Quantitative research assistants will conduct the phone follow-up interviews using an EDC mobile application. Personally identifiable information (PII) will be used for contacting caregivers. A window of +3 days (Day 7 to Day 10) applies to Day 7.

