7.2.1 Data flow, storage and transfer

The data management system will process and combine two main data flows: the research data flow, which will be managed by a secure third-party cloud based EDC platform, and the routine consultation data flow, which will be managed by a customized PostGreSQL Server (Unisanté/Wavemind, Lausanne, Switzerland). As illustrated in **Fig. 7**, there will be separate secured databases with restricted access rights for storing and processing CDSA consultation data, research data for each study, PII that are necessary for all research operations, and (possible) linking between the different databases.

- ξ **Study databases** – These databases will contain de-identified quantitative research data collected in study facilities. Unless specified otherwise per country requirements in the DMP, these databases will be hosted on a device owned and maintained by the country research partner.
- ξ **CDSA consultation database** – This database will contain routine consultation data extracted from CDSA in all intervention facilities. CDSA consultation data from study facilities will be de-identified, i.e. a link will exist between these data, the pre-post study database and the identification database. There will be no such link for CDSA consultation data from non-study facilities, which will then be fully anonymised. Unless specified otherwise per country requirements in the DMP, this database will be hosted on a device owned and maintained by the country research partner.
- ξ **Identification database** – This database will contain PII collected in study facilities. It will be kept under strict operating procedures, in particular it will not be shared or accessible outside of the country. The database will be used for generating follow-up call logs and random selection of a purposive sample of caregivers for qualitative studies. It will also be used for flagging possible duplicates in children enrolled in the pre-post study.

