3.4 Sample Size

The sample size for the quasi-experimental pre-post study is calculated separately for each country, based on comparison between pre- and post-intervention periods. The following assumptions are used:

- ξ power 80%
- ξ alpha level of 0.05
- ξ pre-intervention referral to a higher level of care 3%, with a minimum detectable difference of 50%
- ξ pre-intervention antibiotic prescription of 60%
- ξ intra-cluster correlation coefficient (ICC) of 0.005 for referral and 0.05 for antimicrobial prescription
- ξ Kenya – estimated average cluster size of 230 children / month (assuming a cluster ratio of health centres : dispensaries 1:2, with 100 / month in dispensaries and 500 / month in health centres)
- ξ Senegal – estimated cluster size of 170 children per month

For the referral primary outcome, we therefore initially estimated requiring the following sample size:

- ξ Kenya – 17 facilities, recruiting an average of 690 children per quarter per facility, equating to 11,730 children per quarter
- ξ Senegal – 18 facilities, recruiting an average of 510 children per quarter per facility, equating to 9,180 children per quarter

For the antibiotic prescription primary outcome, this would enable a minimum detectable reduction of 18% in Kenya and Senegal.

Following lower than anticipated recruitment in the pre-intervention period, sample size calculation was revised. As a result, two additional facilities were added per country and the pre-intervention period was extended from an initially anticipated 3 months to a 6 – 8 month period. A decision was also taken to target a post-intervention sample size of at least the same as the pre-intervention sample size, as well as a minimum duration of 9 months post-intervention to allow for stabilisation over time and some seasonal overlap of pre- and post-intervention periods.

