4.2 Intervention adherence and Protocol Deviations

While in Kenya pulse oximeter was indicated for all children, in Senegal, pulse oximeter was indicated for all young infants and for older children with cough/difficult breathing or red/yellow IMCI classification. Cough/difficulty breathing and red/yellow IMCI classification are defined two ways, based on signs and symptoms as reported by the caregiver pre-consultation or on diagnosis made by the healthcare provider during the consultation. These definitions are detailed in a separate document and both will be used, separately, to assess intervention adherence.

Adherence will be evaluated on the basis of pulse oximeter and CDSA use when indicated.

- ξ Pulse oximetry adherence will be evaluated primarily using information on SpO2 values from clinical records. Pulse oximetry will be considered used if the RA has found any SpO2 recording (value readable or unreadable). Pulse oximetry will be considered not used if the RA did not find any recorded SpO2. Adherence will be additionally evaluated based on pulse oximetry use as reported by the caregivers.

- ξ CDSA adherence will be evaluated by comparing the number of children enrolled and the number of children recorded into the CDSA database. These data will be used to explore further and in more details adherence to the CDSA, but outside the scope of this SAP and it will be detailed in a separate document.

Adherence will be reported overall and weekly by facility.

The following information will be summarised by arm to evaluate deviations to the study protocol:

- ξ Number and percentage of caregivers for which no Day 7 follow-up was attempted.

More general deviations will be recorded by the study team in a study deviation log and categorised into minor and major.

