6.4 Additional analyses

Primary outcomes will be further presented by adherence and indication groups (e.g. children for which pulse oximetry was indicated and was used, children for which pulse oximetry was indicated but was not used, etc.).

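### SAP 4.2 measures CDSA adherence from two totals that cover different children; it should use enrolled consultations with a linked CDSA record

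*SAP*

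**What the plan says.** SAP 4.2 sets out two adherence measures. Pulse oximetry is classified child by child, from whether the research assistant found any SpO2 entry. The CDSA measure is different in kind: "CDSA adherence will be evaluated by comparing the number of children enrolled and the number of children recorded into the CDSA database". The SAP then leaves more detailed exploration of CDSA adherence to a separate document, and says adherence will be reported overall and by facility and week.

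The protocol describes what is in the CDSA database. In Protocol 6.3, "Healthcare providers will use ePoct+ for the assessment, diagnosis and management of all sick children 0 – 59 months of age"; the only stated exception is children attending routine visits who are not unwell. Protocol 7.2.1 says of the CDSA database: "This database will contain routine consultation data extracted from CDSA in all intervention facilities". Protocol section 5 adds: "The intervention will be implemented in approximately 60 health facilities providing primary care services", with the pre-post study in only a subset of them.

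The protocol also provides the means for a child-level measure. In the post-intervention period, "the research data of participants enrolled in the study will be linked with their CDSA consultation data" (Protocol 7.1.1). Protocol 7.2.1 confirms that the link exists for study facilities and not for the others. Under Protocol 6.5.1 the research assistant also records whether the CDSA was used for each enrolled child.

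SAP 4.3 reports safety by use of the intervention as section 4.2 defines it, and SAP 6.5 refers back to that.

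**The concern.** The enrolled children are a subset of those for whom the CDSA is used. Enrolment leaves out children whose caregivers refuse or are underage (SAP 5.3), repeat visits within 28 days and trauma-only visits (SAP 5.2), and children for whom consent is not possible after emergency care (Protocol 9.3.1). It also leaves out most visits outside recruitment hours: "Participants will be recruited during working hours, Monday to Friday" (Protocol 6.7, with evenings and weekends added only where volumes are high). Any of these children may have a CDSA record.

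Two things are at stake. First, adherence is what a reader uses to interpret a small or null effect, and a figure that depends on the recruitment rate is a poor guide to whether the tool was used. Second, a comparison of totals says nothing about any one child, so it cannot supply the user and non-user groups for the safety summary. The second problem does not depend on the direction of any bias.

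**Working it through.** The documents give no CDSA adherence figure, so there is nothing to reproduce. The check is what the stated comparison returns if it is taken literally, as records over enrolments.

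**Inputs.** u_e and u_n are true CDSA use in enrolled and non-enrolled children; r is the enrolled share of CDSA-eligible consultations. None is given in the documents, so all values below are assumptions. Study facilities: SAP 3.4 gives 17 in Kenya and 18 in Senegal, and then "two additional facilities were added per country", so 17 + 2 = 19 and 18 + 2 = 20, or 39 in total. Intervention facilities: about 60, without saying whether per country or overall.

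**1. Non-enrolled children in the numerator.** Per enrolled consultation there are (1 − r)/r non-enrolled ones, so

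ratio = u_e + u_n × (1 − r)/r.

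With equal use u this is u/r, which exceeds 100% whenever u > r.

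| True use | r = 0.9 | r = 0.8 | r = 0.7 | r = 0.5 |
|---|---|---|---|---|
| 50% | 55.6% | 62.5% | 71.4% | 100.0% |
| 70% | 77.8% | 87.5% | 100.0% | 140.0% |
| 90% | 100.0% | 112.5% | 128.6% | 180.0% |

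Equal use is not essential. If non-enrolled children have half the use, u_e = 0.9 and r = 0.7 give 0.9 + 0.45 × 0.3/0.7 = 109.3%.

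**2. Recruitment appearing as adherence.** Hold true use at 60%. A facility-week with r = 0.8 reads 0.6/0.8 = 75%; one with r = 0.6 reads 0.6/0.6 = 100%. Use has not changed; only recruitment has.

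**3. Non-study facilities.** If these were also counted, with equal volumes assumed, the overall numerator would grow by 60/39 = 1.54 times, or by 60/20 = 3.0 to 60/19 = 3.16 times if the 60 are per country. Facility-level figures would not have this component.

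**4. Counting unit, in the other direction.** Under Protocol 7.2.2 a patient has one CDSA identifier at a facility and a new case at each visit. Under Protocol 7.2.4 a child who returns after more than 28 days is enrolled again with a new study number. If CDSA patients are counted once, with m CDSA consultations per patient, and enrolments are counted by episode, true use is multiplied by 1/(r × m):

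- m = 1.1, r = 0.9: 1/0.99 = 1.01
- m = 1.1, r = 1.0: 1/1.10 = 0.91
- m = 1.3, r = 0.8: 1/1.04 = 0.96

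So the overall figure can come out too low. Protocol 7.3.1 expects repeat visits to be fairly unlikely, which would keep m close to 1. Within one facility-week this effect has little room, because two enrolments of the same child must be more than 28 days apart.

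**5. After linkage.** With the numerator limited to enrolled consultations that have a linked record, and complete linkage, the measure equals u_e and cannot exceed 100%. True use of 70% reads 70%, against 100.0% (r = 0.7) or 140.0% (r = 0.5) from unlinked totals.

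**The case against.** The best defence is that SAP 4.2 does not prescribe a ratio of unlinked totals. SAP 1.1 says the plan follows the protocol unless stated otherwise, the protocol plans the link, and the children recorded could be read as enrolled children found in the CDSA database. This stands in part: a reader might infer that reported adherence will be overstated, and the documents do not support that. It follows only if the counts are unlinked, and even then the counting unit can work the other way. What remains is that the SAP does not state the linked reading, although its own purpose (SAP 1.1) is to let someone else run the analysis.

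A second defence is that the detail is deferred. The deferral covers further exploration only; the count comparison is the measure reported under this SAP.

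A reader might also infer that SAP 6.4 cannot be carried out: "Primary outcomes will be further presented by adherence and indication groups". Its only examples concern pulse oximetry, which is already defined per child, so that section is not good evidence of a gap.

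Finally, other sources would limit the harm. Research assistants record CDSA use for each child, and the service provision assessments observe it directly, though in only 8–10 facilities per country. A figure above 100% would reveal itself. A figure of 75% where the truth is 60% would not.

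**Conclusion.** The concern holds as a defect of definition. The numerator of the CDSA adherence measure is not limited to enrolled children, study facilities or one counting unit, and the database it comes from is wider than the study. An unlinked comparison can therefore misstate adherence, usually upwards and possibly above 100%; the counting-unit mismatch can offset or reverse this in the overall figure. The size cannot be known from the documents: every value of u, r and m above is an assumption, and the facility multipliers also assume equal volumes.

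Independently of direction, two totals cannot classify a child as a CDSA user for the safety summary in SAP 4.3.

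A reader might go on to infer that the main results are compromised. They are not: SAP 4.3 applies intention to treat to all analyses, so no primary estimate depends on this measure. The effect is on how those estimates are interpreted and on the safety breakdown by use.

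**What to change.** In SAP 4.2, define CDSA adherence as the number of enrolled post-intervention consultations at study facilities that have a linked CDSA record for the same child and consultation date, divided by all enrolled post-intervention consultations at those facilities. Report it overall and by facility and week, with the enrolled consultation as the single counting unit. Use the same child-level indicator for the safety summary in SAP 4.3.

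Report unlinked enrolments separately, and cross-tabulate them against the CDSA use recorded by the research assistant (Protocol 6.5.1).

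The cost is small, since both the link and the research assistant's record are already planned. The downside is that failed links understate adherence by an unknown amount. Protocol 7.2.4 itself notes that identifiers may differ between visits and plans fuzzy matching with manual validation. The cross-check would show this, as enrolments without a link but with recorded use. The linked indicator must be derived before the mapping database is destroyed (Protocol 7.2.1).

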4.3 Analysis Populations

All analyses will follow the intention to treat (ITT) principle, irrespective of any protocol violations.

No safety set will be defined but safety information will be reported overall and by use of intervention as defined in section 4.2.

5 STUDY POPULATION

5.1 Screening

No specific screening data will be captured, aside from those required to assess children's eligibility for the study (see section 5.2). The number of potential participants screened for the study will be presented in a flowchart for pre and post intervention period.

